7.1 Source Data Documentation

Source documents will be the patient's electronic patient record, electronic data entered into the smart phone application and participant questionnaires.

7.2 Case Report Forms

A paper case report form will be generated for each patient and kept in a locked facility at the Rheumatic Diseases Unit at the Western General Hospital Edinburgh.

8 STATISTICS AND DATA ANALYSIS

8.1 SAMPLE SIZE CALCULATION

This is a feasibility study which is intended to establish whether the proposed self-management approach can be realised in practice, and if so to inform the design of a larger study that would look to establish the cost-effectiveness of this approach.

The numbers chosen are based on previous audits in primary care performed which revealed that only 24% of gout patients reached a target of 0.30mmol/l of serum urate when receiving standard care by GPs who were given an algorithm for management of gout beforehand. We have assumed that about 25% of patients assigned to routine care will achieve the target of 0.3mmol/l in the control group. We are anticipating that we will achieve target levels of urate in 75% of patients in the intervention group which though ambitious is still well below the 92% achieved in a recent UK study (Rees, F. 2013). Based on these estimates a sample size of n=34 in the intervention group and n=17 in the control group (2:1 randomisation) provides 82% power to detect an effect of 25% in the control group and 75% in the intervention group (assuming a two-sided 5% significance level), after taking into account a 15% drop-out rate.

For the extension study we have assumed that 90% of participants in the Smart care arm of the study remain adherent to therapy, compared with only 50% in the usual care arm. These figures are conservative compared to 95% compliance reported in Doherty et al (2018) and 36.8% medicine possession ratio reported in Briesacher et al (2008). A sample size of 20 in each allocation yields 81% power, and 30 in each treatment allocation 94% power to detect such a difference. Due to observed drop outs from the feasibility study and restrictions in recruiting participants during the COVID pandemic we will recruit additional participants into the extension phase of the study to ensure sufficient power is achieved.

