4 STUDY POPULATION

4.1 NUMBER OF PARTICIPANTS

We aim to recruit approximately 60 participants. Recruitment will remain open until sufficient numbers of recruited participants has been reached. Additional participants satisfying the same inclusion and exclusion criteria (but without any urate threshold requirement) will be recruited into the extension study to ensure sufficient power is maintained). An equal number of control participants will be recruited for the purposes of the gut microbiota analysis.

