8.2 PROPOSED ANALYSES

The primary outcomes of the study will be the proportion of participants achieving urate level $\leq 0.3\text{mmol/l}$ at 24 weeks in participants receiving supported self-management compared to those receiving usual care. Comparison of proportions will be performed using the Chi-square test of independence, or Fishers Exact test for where expected values in any cell of the contingency table are less than 5, with results displayed as frequency (percentages). The proportion of participants achieving serum urate level $\leq 0.3\text{mmol/l}$ at all subsequent assessments will be analysed in the same fashion. Patients with undetectable levels of oxypurinol will be deemed to be non-compliant and a similar analysis will compare the proportion of participants in each treatment allocation that are non-compliant. For these analyses an intention to treat analysis will be performed with participants that have dropped out of the study being included as failing to reach target, or non-compliant with medication respectively.

Continuous outcome measures include the size in mm of the largest tophus at baseline (index tophus) measured at 52 weeks, and the number of clinically evident tophi evaluated at 52 weeks. Further continuous outcomes include the number of days lost at work due to gout flare, number of scheduled and unscheduled medical appointments/ hospital admissions, self report of number of doses of medication omitted in 2 weeks prior to study visits at week 24 and 52. Two-tailed independent student t-tests will be applied for between group comparisons of normally distributed data. Results will be displayed as mean \pm standard deviation (SD). A Mann Whitney U test (MWU) will be applied when the variables are not normally distributed, with results given as median (interquartile range IQR). Although a nominal value of significance of $p<0.05$ for these exploratory measures will be adopted, given the number of secondary outcomes listed a Bonferroni correction will be applied and reported alongside each result.

Although health reported quality of life data will be gathered this is exploratory data that will not be analysed directly but be used to inform the design of a larger health economic study.

Statistical analysis will be performed using Minitab version 16 (Minitab Inc., Pennsylvania, US) or the Statistical Package for Social Services version 19 (SPSS IBM Corp, NY State, US).

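### The extension's 81% and 94% power contains no visible dropout step, while section 8.2 counts dropouts as non-compliant and no extension dropout rate is stated

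*Combined protocol and SAP*

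**What the plan says.** Section 8.1 sets the extension's assumptions: "we have assumed that 90% of participants in the Smart care arm of the study remain adherent to therapy", against 50% in usual care. It adds: "These figures are conservative compared to 95% compliance reported in" the cited randomised trial of nurse-led care. The power statement follows: "A sample size of 20 in each allocation yields 81% power, and 30 in each treatment allocation 94% power to detect such a difference". No significance level, test or dropout rate is given for the extension. The main-phase calculation in the same section is described as made "after taking into account a 15% drop-out rate".

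Section 8.1 then promises that "we will recruit additional participants into the extension phase of the study to ensure sufficient power is achieved", giving main-phase dropouts and the pandemic as reasons. Section 4.1 says likewise that further participants "will be recruited into the extension study to ensure sufficient power is maintained". Neither gives a number.

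Section 8.2 treats undetectable oxypurinol as non-compliance and says "a similar analysis will compare the proportion of participants in each treatment allocation that are non-compliant". The analysis is by intention to treat, with "participants that have dropped out of the study being included as failing to reach target, or non-compliant with medication respectively". The test is chi-square, or Fisher's exact test when an expected cell count is below 5.

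**The concern.** Under the 8.2 rule a dropout is not removed from the comparison. The person stays in the denominator and counts as a failure, so dropout lowers the adherence proportions being compared. If 90% and 50% describe adherence before dropout, the power quoted in 8.1 belongs to a more favourable comparison than the one that will be analysed.

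This matters because long-term compliance is a stated purpose of the two-year extension (section 3.2), and because extra recruitment is open-ended and tied to power being sufficient. The figures for 20 and 30 per arm are the only yardstick for when to stop recruiting. The 24-week primary endpoint is not affected.

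**Working it through.** **Inputs.** From 8.1: adherence 0.90 and 0.50, with 20 or 30 per arm. From 8.2: chi-square with the switch to Fisher's exact test, and dropouts counted as non-compliant. Assumed: two-sided 5%, which 8.1 states only for the main phase; that 8.1's adherence is 8.2's compliance endpoint; and every extension dropout rate below.

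**1. Reproducing the stated power.** Pooled normal approximation, with p̄ = 0.70:

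power = Φ{ [0.40 − 1.96·√(2·0.70·0.30/n)] / √[(0.90·0.10 + 0.50·0.50)/n] }

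- n = 20: (0.40 − 1.96·0.1449)/0.1304 = 0.889, so power is 81.3%.
- n = 30: (0.40 − 1.96·0.1183)/0.1065 = 1.579, so power is 94.3%.

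Both match 8.1 with no dropout step. One other route also rounds to the stated figures: the unpooled formula after removing 15% (17 and 26 per arm) gives 80.7% and 93.8%. That route takes dropouts out of the denominator, so it is not the 8.2 analysis either. Exact power of the 8.2 test at 17 and 26 per arm is 71.7% and 92.3%.

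**2. Applying the 8.2 rule.** With dropout d₁ (active) and d₂ (usual care), independent of adherence, the compared rates are 0.90(1 − d₁) and 0.50(1 − d₂) on the full n. Power is by exact enumeration of the 8.2 test.

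| Dropout, active / usual care | Rates compared | 20 per arm | 30 per arm |
|---|---|---|---|
| 0% / 0% | 0.900 vs 0.500 | 82.7% | 94.9% |
| 5% / 5% | 0.855 vs 0.475 | 75.8% | 89.9% |
| 10% / 10% | 0.810 vs 0.450 | 67.8% | 84.1% |
| 15% / 15% | 0.765 vs 0.425 | 59.7% | 78.1% |
| 20% / 20% | 0.720 vs 0.400 | 52.1% | 72.2% |
| 20% / 10% | 0.720 vs 0.450 | 40.1% | 57.3% |
| 10% / 20% | 0.810 vs 0.400 | 78.0% | 92.0% |
| 5% / 15% | 0.855 vs 0.425 | 84.7% | 95.3% |

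With equal dropout, power falls below 80% at 3% for 20 per arm (78.7%) and at 14% for 30 per arm (79.3%).

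**3. Dropout related to adherence.** If 15% leave each arm and the non-adherent leave first, the active rate is capped at 0.85 and usual care stays at 0.50. Power is then 68.8% and 84.7%.

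**4. When the rates can be net of dropout.** Under 8.2 the active-arm rate cannot exceed 1 − d₁. So 0.90 ≤ 1 − d₁, which gives d₁ ≤ 10%.

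**5. Size needed for 80% with equal dropout.** 23 per arm at 5%, 26 at 10% and 31 at 15%. Ordinary inflation is not enough: 20/0.85 rounds up to 24 per arm, which gives 70.5% at 15% dropout, because dropouts remain as failures.

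**The case against.** The strongest reply is that 8.1 takes all participants in the arm as its denominator, which is also the intention-to-treat denominator of 8.2. On that reading 90% and 50% already include dropouts, and 81% and 94% stand. The text allows this and does not settle it. What remains is that the reading carries an unstated limit of 10% on active-arm dropout.

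A reader might infer that the stated power must be too high whenever the rates are not net. The documents do not support that, because they give no dropout by arm. Usual-care participants have no further titration or outpatient review once at target (section 3.2), so higher dropout there is plausible, and at 5% versus 15% power exceeds the stated figures. Part of that difference would then be retention rather than adherence.

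A reader might also tighten the limit to 5.3% (1 − 0.90/0.95) by capping adherence among those retained at the 95% cited in 8.1. The section uses that figure only to call its own assumption conservative, and does not say whether it refers to retained patients.

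The 15% is a main-phase planning rate. Continuing participants have completed week 52 and may stay better, although additional recruits need not. Section 8.1 also does not tie its adherence to the oxypurinol definition, and section 2.2.2 measures oxypurinol only where possible. Finally, the comparison is secondary, in a feasibility study, and extra recruitment is already planned, though without a number.

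**Conclusion.** The point holds in conditional form, as a minor issue. The arithmetic in 8.1 is correct for the inputs used; what is missing is an extension dropout assumption consistent with 8.2. Taking 8.1's adherence as 8.2's compliance endpoint, and unless 90% and 50% are net of dropout, the stated power is too high when dropout is similar across arms or higher in the active arm. The equal-dropout loss from the stated 81% and 94% is about 5 and 4 percentage points at 5% dropout, 13 and 10 at 10%, and 21 and 16 at 15%. With sufficiently higher dropout in usual care there need be no loss. All these dropout rates are assumed, as is the two-sided 5% level. The point deserves correction because these two figures are the only stated guide to how many more participants to recruit.

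**What to change.** In 8.1, restate the extension power with dropouts counted as non-compliant, as 8.2 requires, over a stated range of dropout rates (for example 5% to 20%, equal and unequal by arm). Name the significance level, the test and the adherence endpoint, and make that restated power the yardstick for sufficient power in 4.1 and 8.1. If 90% and 50% are meant net of dropout, say so and give the dropout rate this implies; 81% and 94% can then stay.

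The cost is one or two sentences. The first course may give a less favourable power for a secondary comparison; the second commits the plan to active-arm dropout of at most 10%. The analysis in 8.2 does not change.

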8.2 PROPOSED ANALYSES

The primary outcomes of the study will be the proportion of participants achieving urate level $\leq 0.3\text{mmol/l}$ at 24 weeks in participants receiving supported self-management compared to those receiving usual care. Comparison of proportions will be performed using the Chi-square test of independence, or Fishers Exact test for where expected values in any cell of the contingency table are less than 5, with results displayed as frequency (percentages). The proportion of participants achieving serum urate level $\leq 0.3\text{mmol/l}$ at all subsequent assessments will be analysed in the same fashion. Patients with undetectable levels of oxypurinol will be deemed to be non-compliant and a similar analysis will compare the proportion of participants in each treatment allocation that are non-compliant. For these analyses an intention to treat analysis will be performed with participants that have dropped out of the study being included as failing to reach target, or non-compliant with medication respectively.

Continuous outcome measures include the size in mm of the largest tophus at baseline (index tophus) measured at 52 weeks, and the number of clinically evident tophi evaluated at 52 weeks. Further continuous outcomes include the number of days lost at work due to gout flare, number of scheduled and unscheduled medical appointments/ hospital admissions, self report of number of doses of medication omitted in 2 weeks prior to study visits at week 24 and 52. Two-tailed independent student t-tests will be applied for between group comparisons of normally distributed data. Results will be displayed as mean \pm standard deviation (SD). A Mann Whitney U test (MWU) will be applied when the variables are not normally distributed, with results given as median (interquartile range IQR). Although a nominal value of significance of $p<0.05$ for these exploratory measures will be adopted, given the number of secondary outcomes listed a Bonferroni correction will be applied and reported alongside each result.

Although health reported quality of life data will be gathered this is exploratory data that will not be analysed directly but be used to inform the design of a larger health economic study.

Statistical analysis will be performed using Minitab version 16 (Minitab Inc., Pennsylvania, US) or the Statistical Package for Social Services version 19 (SPSS IBM Corp, NY State, US).

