2.2 ENDPOINTS

2.2.1 Primary Endpoint

- Proportion of participants achieving urate level $\leq 0.30\text{mmol/L}$ at 24 weeks.

2.2.2 Secondary Endpoints (assessed at week 24 and 52, and for extension study also at week 104 and 156)

- Proportion of participants achieving urate level $\leq 0.3\text{mmol/l}$ and $\leq 0.36\text{mmol/l}$
- Prospectively gathered number of days of self-reported gout flare over course of study
- Size in mm of the largest tophus at baseline (index tophus)
- The number of clinically evident tophi
- Prospectively gathered self-reported quality of life during/following gout flare evaluated using the EQ-5D-5L questionnaire over course of study
- Prospectively gathered data on days lost at work due to gout flare over course of study
- Prospectively gathered number of scheduled and unscheduled medical appointments/ hospital admissions due to gout over course of study
- Self report of number of doses of medication omitted in preceding 2 weeks will be collected at all study visits
- Plasma oxypurinol levels will be measured at study visits where possible
- Proportion of patients achieving a dose reduction of urate lowering therapy in the extension phase whilst maintaining target urate levels.
- Proportion of patients achieving sustained dietary modifications with reduction of urate levels, and/or further reduction of urate lowering therapy dose in the extension phase.

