The main outcome will be urate levels at week 24, with a secondary outcome being urate levels at week 52. Where participants are able to attend hospital then both serum and capillary urate will be obtained and the serum urate will be used as the study outcome, however we anticipate that a capillary urate only will be obtained in participants required to self-isolate or maintain social distancing during the coronavirus pandemic and this will be used to determine the urate level at week 24 and 52 for affected participants. To assess treatment compliance drug metabolite levels will be tested from serum samples obtained at week 24 and 52 visits where possible, and by self report in all participants. All patients will be assessed for tophi at baseline by clinical exam, and again at week 24 and 52. This will be by examination if participants are able to attend hospital, or by review of submitted images where attendance at hospital is not appropriate due to coronavirus restrictions. All participants will be asked once per month to record flares, measurements of quality of life, number of hospital and GP visits as well as days off work via the application. The study is designed for a total (post-randomization) duration of 52 weeks. Subjects who withdraw or disengage before the 24 week visit will not be considered to have completed the study.

For the gut microbial aspect of this study, eligible participants will fill in an online semi-quantitative food frequency questionnaire (FFQ, Scottish Collaborative Group – see Zgaga et al, PLOSone 2012). Patients will also provide an early morning urine sample for urinary metabolomic analysis and a fresh faecal sample for subsequent faecal metabolomics and shotgun metagenomics. To provide suitable controls, patients will be asked whether they are happy that a family member be contacted to provide control samples for this analysis. In this case, first or secondary sex-matched controls without gout will be contacted by the study team for a once-off visit (Medical history, bloods – serum urate LFTs, renal function, FFQ and urine and stool samples). Patients can opt out of having a family member involved if they wish in which case local controls (age-similar and sex matched) will be recruited from the staff of the University of Edinburgh.

Figure 1: Study Design

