6 STUDY PROCEDURES AND ASSESSMENTS

6.1 STUDY PROCEDURES

6.1.1 Baseline visit

Written and informed consent will be obtained. A history will be taken, basic anthropometric measurements taken (blood pressure, weight, waist circumference) and physical examination be performed. Full medication history will be obtained from participants. Blood samples will be taken for measurement of urate, full blood count, renal and liver function and oxypurinol levels. A finger prick testing for urate levels will be carried out. Participants will be asked to collect urine over a period of 24hrs to hand into the lab as soon as feasible after the baseline visit. A blood sample for creatinine and urate will be taken at that point for paired analysis with urine. Eligible subjects will be randomised at a 1:2 ratio to usual care or supported self-management using a web-based randomisation tool.

For the purposes of the microbiome analysis, patients will provide a once off stool and urine sample at baseline in addition to filling an online food frequency questionnaire. For control subjects for the microbiome analysis, participants will attend on one occasion to provide written informed consent, medical history review, FFQ, blood samples for urate, renal and liver function and oxypurinol levels. In addition they will provide an early morning urine sample and a fresh faecal sample. They will also be asked to collect urine over the 24hour period and a paired serum renal function and urate blood sample will be taken when handing the collection in. No further follow-up visits are planned.

No payment shall be made for participation in the study but compensation for costs of travel to the Western General Hospital shall be offered to control participants up to a value of £30

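### The primary analysis commits to a p-value and percentages only: no treatment difference, no confidence interval, no use of baseline urate and no analysis of week-24 urate as a measured value

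*Combined protocol and SAP*

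**What the plan says.** **Test and display.** Section 8.2 compares the arms on the proportion at target at week 24: "Comparison of proportions will be performed using the Chi-square test of independence", or Fisher's exact test where an expected count is below 5, "with results displayed as frequency (percentages"). Dropouts count as failures under intention to treat. The section names no covariate, risk difference, ratio or confidence interval.

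**Urate as a value.** Section 3.1 states: "The main outcome will be urate levels at week 24, with a secondary outcome being urate levels at week 52". The endpoints in 2.2 are nevertheless all proportions below a cut-off as far as urate is concerned, and the continuous outcomes listed in 8.2 do not include urate.

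**Baseline.** Under 6.1.1, "Blood samples will be taken for measurement of urate", and a finger-prick urate is taken as well. Serum urate above 0.36 mmol/L is an entry criterion (4.2). Both measurement methods are therefore available at baseline.

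**Purpose.** Section 8.1 says that the study should, if the approach proves workable, "inform the design of a larger study". Section 13.2 calls this the immediate goal.

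**The concern.** A study that feeds the design of a larger trial is most useful for its estimate of the effect and the uncertainty around it. For continuous urate, the next team also needs the standard deviation and the correlation with baseline. The plan commits to none of these.

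The plan also sets information aside. Starting urate plausibly affects who reaches 0.30 mmol/L, and a yes/no outcome treats a participant just above the cut-off like one far above it. With about 60 participants randomised 2:1 (40 v 20), the difference in mean baseline urate between arms has a standard error of √(1/40 + 1/20) = 0.27 SD, so a noticeable chance imbalance would not be unusual.

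**Working it through.** **Inputs from the documents.** Target rates 75% v 25%, 34 v 17, two-sided 5%, 15% dropout (8.1). Approximately 60 participants (4.1) at 2:1 (3.1), so 40 v 20. Dropouts as failures (8.2).

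**Assumptions not in the documents.** Urate is normal with equal SD in both arms. The correlation r between baseline and week 24 is 0.3 to 0.7. Dropout is random. 65% v 35% serves as an example of a smaller effect; 8.1 itself calls the 75% ambitious.

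**1. The plan's own figure.** After 15% dropout about 29 v 14 remain. Continuity-corrected formula for two proportions:
- corrected difference = 0.50 − 0.5 × (1/29 + 1/14) = 0.447
- pooled rate = (29 × 0.75 + 14 × 0.25)/43 = 0.587, so null SE = √(0.587 × 0.413 × 0.1059) = 0.160
- alternative SE = √(0.1875 × 0.1059) = 0.141
- power = Φ[(0.447 − 1.96 × 0.160)/0.141] = Φ(0.944) = 82.7%

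The stated 82% reproduces. The chi-square/Fisher rule as written in 8.2 has about 90% at 29 v 14. With 15% dropouts counted as failures it has about 87% at 34 v 17 and 91% at 40 v 20.

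**2. The interval that is not promised.** Wald: difference ± 1.96 × √[p₁(1−p₁)/n₁ + p₂(1−p₂)/n₂].

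| Scenario | Difference (points) | 95% CI |
|---|---|---|
| 34 v 17, 75% v 25% | 50 | 25 to 75 |
| 34 v 17, dropouts as failures (63.75% v 21.25%) | 42.5 | 17 to 68 |
| 40 v 20, 75% v 25% | 50 | 27 to 73 |
| 40 v 20, 65% v 35% | 30 | 4 to 56 |

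The first row: √(0.1875/34 + 0.1875/17) = 0.129, and 0.50 ± 1.96 × 0.129 = 0.25 to 0.75. All four intervals are roughly 45 to 55 points wide, which a p-value beside two percentages does not show.

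**3. Power at a smaller effect.** Simulation at 40 v 20 and 65% v 35%. The adjusted binary analysis is a linear model of success on arm and baseline urate with HC3 robust errors. ANCOVA uses completers.

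| Analysis | No dropout | 15% dropout |
|---|---|---|
| Plan's test | about 61% | about 48% |
| Adjusted binary, r = 0.3 to 0.7 | 59% to 74% | 47% to 56% |
| ANCOVA of week-24 urate, r = 0.3 to 0.7 | 82% to 97% | 76% to 94% |

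The right-hand column applies the plan's dropout rule to the binary analyses and is the relevant one. Null rejection for the adjusted analyses stayed close to 5% (about 4% to 6% across runs).

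**4. Analytic check on ANCOVA.** The two rates differ by 0.385 + 0.385 = 0.771 SD. Completers are 0.85 × 40 = 34 and 0.85 × 20 = 17. Power ≈ Φ[0.771 × √(34 × 17/51)/√(1 − r²) − 1.96] = Φ[2.595/√(1 − r²) − 1.96]. This gives 78%, 85% and 95% at r = 0.3, 0.5 and 0.7. That is slightly above the simulation, as expected of a normal approximation.

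**5. Logistic adjustment.** At 34 v 17 or 29 v 14, a logistic likelihood-ratio test adjusted for baseline rejected in about 6% to 7% of null runs, so part of its apparent gain is spurious.

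**The case against.** **The endpoint is a sound choice.** 0.30 mmol/L is the treatment goal for every participant (3.1), and dropout-as-failure fits a binary outcome. This stands, and there is no reason to replace it.

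**The counts are shown.** Anyone can derive a crude difference and interval from counts by arm. This is true, so no crude information is lost, but an estimate left to readers is not a prespecified result. An adjusted estimate, the SD and the baseline correlation cannot be recovered from the counts.

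**Adjusting the binary endpoint gains little.** This stands. Below r of about 0.5 there is no real gain in power, and a point or two may be lost. The case for adjustment is an estimate that accounts for chance baseline differences, with more precision only if the correlation is high.

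**ANCOVA answers another question.** This also stands. Its 76% to 94% is power for a difference in mean urate. A reader might infer that the plan throws away that much power on its primary endpoint, but power for a mean is not power for the proportion at target. ANCOVA also cannot use dropout-as-failure and needs its own rules for missing values and for mixed serum and capillary readings.

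**Imbalance does not bias the test.** A reader might infer that an unadjusted test is invalid here, or that randomisation is unstratified. Under randomisation the test is valid, and its error rate already allows for chance imbalance. Section 6.1.1 mentions a web-based tool and is silent on stratification, which does not show that there is none.

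**Conclusion.** The point holds as one of estimation and unused information. Section 8.2 commits to no treatment difference or interval for the primary endpoint, leaves baseline urate unused, and plans no continuous analysis of week-24 urate, in a study whose declared purpose is to inform a larger trial. The missing estimate and interval is the stronger part and depends on no outside assumption: at the planned rates the interval is about 50 points wide at 34 v 17.

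The tempting stronger conclusion, that the trial is underpowered, is not supported. The stated 82% reproduces, and the planned test does at least as well at 75% v 25%. The power comparison matters only for a smaller effect, and it rests on assumed normality, random dropout and r of 0.3 to 0.7. The change should be made but is not critical.

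**What to change.** In 8.2:
- Keep the endpoint of 0.30 mmol/L or below, dropout-as-failure, and chi-square/Fisher as the simple test.
- Report the risk difference with a 95% CI, adjusted for baseline urate by a linear risk-difference model with HC3 robust errors. Name this model first, because a logistic fit may be unstable with few control successes (25% of 17 to 20 is about 4 to 5). Give the crude difference and its 95% CI alongside.
- Add ANCOVA of week-24 urate on baseline urate, labelled as a supporting analysis of a different quantity (mean urate). Report the SD and the baseline correlation with it.
- For the ANCOVA, use one method for outcome and baseline within each participant: serum where available, otherwise capillary. Include method as a covariate, or add a serum-only sensitivity analysis.
- State that the ANCOVA uses participants with an observed week-24 value and assumes that missing values are missing at random.

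The cost is SAP wording and slightly more analysis, with no new visits, samples or participants. The downside is little or no power gain for the binary endpoint, possibly a point or two lost, if the baseline correlation is low.
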